**Table 1. Registry Activities (Continued)**

- f. AESI, SAEs and pregnancies will be collected from Year 1 through Year 5. From Year 6 through Year 10 SAEs, a subset of AESI that includes congestive heart failure (CHF), malignancies, AEs at least possibly related to and/or leading to discontinuation of registry treatment and pregnancies will be collected. For patients that participate in the direct to HCP follow-up process AESI, hospitalizations, surgeries, and death will be collected annually from Year 1 through Year 5 and malignancies, CHF, hospitalizations, surgeries and death will be collected annually from Year 6 to Year 10. For polyarticular JIA patients from 2 to < 4 years of age while in the registry AESI, SAEs and pregnancies will be collected through Year 10 and those who participate in the direct to HCP follow-up process will have AESI, hospitalizations, surgeries and death collected annually through Year 10.
- g. Provide local lab values including but not limited to ESR, CRP, anti-nuclear antibody (ANA), and any labs related to SAE's or AEs of Special Interest (i.e., CPK, presence of lupus anticoagulants or anticardiolin antibodies). The assessments will be collected at baseline and afterwards only when part of physician's site routine care.
- h. Patients who develop an Adverse Event of Special Interest (AESI) or SAE while in the registry will be followed throughout the patient's participation in the registry or direct to HCP follow-up process until satisfactory conclusion or until 70 days following the last registry dose (whichever is longer). Follow-up received on ongoing SAEs and/or AESI post registry conclusion should be reported using standard Post Marketing Reporting.

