### 10.3 Safety Analyses

Four safety summaries will be reported from this registry.

Observational AEs: SAEs and AEs of Special Interest occurring from the first day in registry through the last contact (see definition in Section 10.3.1) irrespective of drug treatment duration.

Registry Treatment-Emergent AEs: SAEs and AEs of Special Interest occurring from the first dose in the registry through the last dose plus 70 days in the registry, excluding AEs occurring during TI period.

All Treatment Emergent AEs: SAEs and AEs of Special Interest occurring from the first recorded dose (initial dose) of MTX or Humira through the last dose plus 70 days in the registry, excluding AEs occurring during TI period. For patients enrolled from Study M10-444 and Study DE038, the total number of SAEs and AEs of Special Interest will include the events reported after the

first recorded dose of study drug in previous study, except those which occurred during the double-blind period in Study DE038 if the patient was in the Placebo arm during this period, any events reported by retrospective data collection, and events reported during this registry.

AEs for intermittent treatment: SAEs and AEs of Special Interest in the Intermittent Treatment Population through 10 years of the registry.

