### **10.3.4 Analysis of Patients with Treatment Interruption (TI)**

The following summaries will be performed for patients with a treatment interruption (TI) in Humira injections. The SAEs and AEs of Special Interest collected through the HCP process will not be included in these summaries.

For the first group of safety summaries, all patients will be categorized into 2 groups: patients who have at least one TI and patients who have no TI. Two summaries of SAEs

and Adverse Events of Special Interest will compare descriptively patients who have at least one TI and patients who have no TIs:

Crude incidence: The number and percent of patients experiencing SAEs or Adverse Events of Special Interest will be tabulated for each SOC and PT.

Events per 100 patient years of observation: The number of SAEs and Adverse Events of Special Interest per 100 patient years of observation will be tabulated for each SOC and PT.

For the second group of safety summaries the longest TI will be considered and adverse event rates (SAE and Adverse Events of Special Interest) during the last on-drug period prior to the TI (i.e., the pre-TI period) will be compared to adverse event rates during the first on drug period following the TI (i.e., the post-TI period).

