**Table 2. Definition of Pre-TI and Post-TI Periods**

	Pre-TI Period	Post-TI Period
Start	First injection of the registry	Day of first injection following the longest TI
End	70 days following the last injection before the longest TI	70 days following registry completion/stop of participation

The preceding summaries do not distinguish between the same adverse events experienced by the same patients pre-TI and post-TI from the same adverse events experienced by different patients pre-TI and post-TI. Therefore, a third summary will evaluate the proportions of patients who report onset of the same adverse event pre-TI and post-TI, patients who report onset only pre-TI, patients who report onset only post-TI, and patients who do not report the event in either period.

For each TI experienced by 1% of patients and for each SAE and Adverse Event of Special Interest, the number and percent of patients who have the event or not before the TI and after the TI will be summarized as shown in [Table 3](#). This assessment will provide information about whether same or different patients experience the adverse pre-TI and post-TI.

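### The 10-year pre-TI versus post-TI comparison of AESI rates crosses the Year 6 narrowing of AESI collection, which pulls the post/pre rate ratio below 1 for patients aged 4 to 17 followed past Year 5

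*Supplement*

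**What the plan says.** **Analysis.** Section 10.3 lists as its fourth safety summary "AEs for intermittent treatment: SAEs and AEs of Special Interest in the Intermittent Treatment Population through 10 years of the registry". Section 10.3.4 takes the longest TI and states that rates of SAEs and AESI in the on-drug period before it "will be compared to adverse event rates during the first on drug period following the TI (i.e., the post-TI period"). Table 2 starts the pre-TI period at "First injection of the registry" and ends the post-TI period at "70 days following registry completion/stop of participation". Then "a third summary will evaluate the proportions of patients who report onset of the same adverse event pre-TI and post-TI", and for Table 3 "the number and percent of patients who have the event or not before the TI and after the TI will be summarized". Data from the HCP process are excluded from all of these summaries.

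**Collection.** Table 1, note f: "AESI, SAEs and pregnancies will be collected from Year 1 through Year 5". The note continues: "From Year 6 through Year 10 SAEs, a subset of AESI that includes congestive heart failure (CHF), malignancies, AEs at least possibly related to and/or" ending registry treatment, together with pregnancies. Sections 6.0, 6.6.5 and 7.1.7 give the same list and make collection annual after Year 5. Patients aged 2 to < 4 keep the full AESI list for 10 years.

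**Not uniform.** A later paragraph of Section 6.6.5, and Section 6.7.2, name only SAEs, CHF and malignancies for Years 6 to 10. Section 7.1.3 opens by saying that AESI are monitored routinely through Year 10, but later ties the additional follow-up after Year 5 to malignancies and CHF.

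Section 10.3.4 contains no Year 5 cut-off, no restriction to event types collected throughout, and no separate display for Years 6 to 10.

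**The concern.** The comparison sets an earlier period against a later one, and what counts as a recordable AESI changes part-way through. Section 7.1.3 includes nonserious opportunistic infections (Candida and Herpes among them) and new or worsening psoriasis. Suppose such an event keeps occurring at the same rate, is nonserious and is judged unrelated. It is recorded in the pre-TI period but not in the part of the post-TI period that lies after Year 5. The person-time stays in the denominator while the event leaves the numerator.

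Section 5.0 makes the effect of treatment interruptions on the safety of Humira a stated objective, and this is the protocol's direct within-patient look at it. An artefact that makes the post-restart AESI rate look lower is an unwelcome direction of error for a post-marketing safety commitment.

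**Working it through.** **1. The protocol's own figure (Section 10.6).** This is the only computed design figure; none is given for the TI comparison. At 1500 patient-years (PY), expected serious infections are 1500 × 0.028 = 42 under the reference rate and 1500 × 0.048 = 72 under the alternative. Normal approximation: (72 − 42 − 1.96 × √42) / √72 = 2.04, power 97.9%. Exact Poisson (reject at 56 or more events) gives 97.8%. The stated 97% reproduces closely. Reading the 68% dropout as exponential loss by Year 5, the hazard is −ln(0.32)/5 = 0.228 per year. That gives 500 × 0.68/0.228 ≈ 1492 PY, which matches the planned 1500, so the hazard is used below.

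**2. How much person-time is exposed.** If the same hazard continues to Year 10 (assumption), Years 6 to 10 add 1492 × 0.32 ≈ 477 PY, or 477/1969 = 24% of the Humira total.

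**3. Formula.** Let q be the share of AESI of the type no longer collected from Year 6, and let a and b be the shares of pre-TI and post-TI time after Year 5. With a constant true rate, the expected recorded rate ratio is

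post/pre = (1 − q·b) / (1 − q·a).

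It is below 1 whenever b > a and q > 0. Table 2 orders the periods in time, so b exceeds a whenever post-TI time runs past Year 5.

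**4. Shares and ratios.** Assumptions: TI length 0.2 to 0.8 years, TI start uniform over the span shown, Table 2 windows, a and b pooled over simulated patients. The documents give neither TI timing nor q.

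| Follow-up | TI start uniform over | a | b | q = 20% | q = 40% | q = 60% |
|---|---|---|---|---|---|---|
| Dropout continued to Year 10 | each patient's own follow-up | 0.101 | 0.444 | 0.93 | 0.86 | 0.78 |
| Dropout continued to Year 10 | Years 0-10 | 0.138 | 0.569 | 0.91 | 0.82 | 0.72 |
| Complete 10 years | Years 0-10 | 0.225 | 0.775 | 0.88 | 0.76 | 0.62 |

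Example, last row at q = 40%: (1 − 0.4 × 0.775)/(1 − 0.4 × 0.225) = 0.690/0.910 = 0.76. With q = 0, or with both periods cut at Year 5 (a = b = 0), the ratio is 1.00.

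**5. Shift table (Table 3).** It counts patients and carries no person-time. Assume 2 events per 100 PY, half of AESI still collected from Year 6, a 0.5-year gap and follow-up to Year 10:

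| Pre-TI period ends at year | Pre-TI only | Post-TI only | Post-TI only if nothing were lost |
|---|---|---|---|
| 1 | 1.8% | 11.1% | 15.3% |
| 2 | 3.5% | 9.1% | 13.4% |
| 3 | 5.4% | 7.2% | 11.5% |
| 4 | 7.2% | 5.4% | 9.6% |

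The narrowing lowers the post-TI count in every row. Which cell is larger depends on period length as well.

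**The case against.** Much of the comparison is sound, and that should be granted.

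- SAEs are collected in full to Year 10, so the SAE rates carry no narrowing bias.
- The lost category is narrow under the fuller wording. An event must be nonserious, judged unrelated, not treatment-ending, and neither malignancy nor CHF. Haematologic and hepatic AESI must be serious or treatment-ending to qualify at all. The related and treatment-ending events most relevant to restart remain.
- The values of q have no source in the documents, and heavy dropout reduces the bias.
- The summary is descriptive and serves a secondary objective.

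A reader might also infer that the shift table is tilted towards safety because its 'pre-TI yes, post-TI no' cell fills up. The documents do not support that: Table 3 has no person-time, and for early TIs the longer post-TI period outweighs the lost events, as step 5 shows. Nor should a reader take it that the later period must contain fewer AESI; the fixed direction applies to rates only.

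Last, no SAP is among the documents, so a restriction there cannot be excluded. That does not dispose of the point, because the protocol itself sets the 10-year span and Section 10.3.4 defers nothing on it to the SAP.

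These arguments limit the scope and size of the problem. They do not remove it.

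**Conclusion.** The point holds for AESI rates in patients aged 4 to 17 followed past Year 5. With no change in true risk, the recorded post/pre ratio is about 0.91-0.93, 0.82-0.86 or 0.72-0.78 for q = 20%, 40% or 60% with the planned dropout continued to Year 10, and about 0.88, 0.76 or 0.62 with complete follow-up. These sizes rest on assumed q, assumed TI timing and a constant true rate; the direction does not depend on the particular values. Under the narrower lists in Sections 6.6.5 and 6.7.2, q would be larger. If the opening sentence of Section 7.1.3 governed, the problem would disappear.

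The size also depends on the post-TI window. The text of Section 10.3.4 uses the first on-drug period after the TI, whereas Table 2 runs to the end of participation plus 70 days. The first reading leaves less late time for a patient with a further TI. For Table 3, the conclusion is only that it mixes two collection regimes. This is a SHOULD-level correction.

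**What to change.** 1. In the pre/post-TI AESI rates and in Table 3, either include only event types collected in both eras (SAEs, CHF, malignancies, and AEs possibly related to or ending treatment), or cut pre-TI and post-TI time at Month 60 for the full AESI list. No cut is needed for patients aged 2 to < 4.
2. Show SAEs separately over the full 10 years.
3. Reconcile the Years 6 to 10 collection lists in Sections 6.0, 6.6.5, 6.7.2, 7.1.3, 7.1.7 and Table 1 note f, since they determine which event types count as collected throughout.
4. Reconcile the post-TI window in the text of Section 10.3.4 with Table 2.

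The cost is analysis wording, with no new data collection. The Month 60 option gives up post-TI years for the full AESI list. Neither option cures the unequal period lengths behind Table 3, so its cells should still not be read as a comparison of risk.

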### **10.3.1 Analysis of Observational SAEs and AEs of Special Interest**

The number and percent of patients experiencing SAEs and AEs of Special Interest during the registry, regardless of whether the AEs are reported during or after the Humira or MTX treatment, will be tabulated by body system and Medical Dictionary for Drug Regulatory Activities (MedDRA®) preferred term. Rates (event per 100 patient year of observation) of SAEs and AEs of Special Interest and the 95% confidence interval will be provided. The AEs summaries will also include SAEs and AEs of Special Interest collected through the HCP process. The last contact date is defined as the last date of registry or direct to HCP process participation, whichever occurs later.

The summaries will be provided using data from the first day in registry through the last contact irrespective of drug treatment duration.

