### **10.3.2 Analysis of Registry Treatment-Emergent SAEs and AEs of Special Interest**

Registry Treatment-emergent SAEs and AEs of Special Interest will be summarized.

Registry Treatment-emergent AEs includes AEs occurring from the first dose day of the registry to 70 days after the last dose of registry drug excluding AEs occurring during TI period. The SAEs and AEs of Special Interest collected through the HCP process will not be included in this summary.

The number and percentage of patients experiencing registry treatment-emergent SAEs and AEs of Special Interest will be tabulated by body system and MedDRA® preferred

term. In addition, a summary of SAEs and AEs of Special Interest by severity and relationship to registry drug will be presented. Rates (event per 100 patient-years of registry exposure to Humira or MTX) of SAEs and AEs of Special Interest and the 95% confidence interval will be provided.

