## **10.6 Determination of Sample Size**

The proposed sample size for this registry is approximately 800 patients. Due to the low incidence and prevalence of the disease, the size of the registry has been chosen based on the expected availability of eligible patients to be enrolled in a three year time frame. The estimated recruitment rates were based on published articles and advice from one leading pediatric rheumatology site.

It is planned that a total of 800 patients will be enrolled to this registry in a ratio of 5:3 corresponding to the Humira arm or the MTX arm respectively. The sample size determination is based on the rate of serious infectious AEs in the Humira arm. Assuming a total of 500 patients with full 5 years of follow up in the Humira arm, a maximum total exposure to the Humira in this registry can be 2500 patient years. Typically a higher rate of dropout is expected in a registry compared to traditional controlled studies. Allowing for approximately 68% dropout, a total of approximately 1500 patient years exposure in the Humira arm will have approximately 97% power, using a two-sided test at level of significance  $\alpha = 0.05$ , to detect a rate of serious infectious AE of 4.8 events per 100 patient years from the rate of 2.8 events per 100 patient years previously seen in this population in Study DE038.

Due to low frequencies of malignancies and congestive heart failure (CHF), patients will be followed for an additional 5 years.

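### The only patient-level safety summary in Sections 10.3.1 to 10.3.3 is a crude percent of patients, which under incomplete follow-up is not a risk at any stated time

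*Supplement*

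**What the plan says.** Protocol Section 10.3.1 (observational summary) tabulates "The number and percent of patients experiencing SAEs and AEs of Special Interest during the registry" by body system and preferred term. It counts events to last contact whatever the treatment, and includes the direct-to-HCP process. Section 10.3.2 does the same within the registry treatment-emergent window: "The number and percentage of patients experiencing registry treatment-emergent SAEs and AEs of Special Interest will be tabulated by body system". Section 10.3.3 repeats this from the first recorded dose. Both treatment-emergent summaries end 70 days after the last dose, leave out treatment interruptions and exclude HCP data.

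All three sections also give events per 100 patient-years with a 95% confidence interval, over observation, registry exposure and total exposure respectively. Section 10.2 summarises duration of observation, exposure and reasons for discontinuation. The protocol describes no Kaplan-Meier, cumulative incidence or other time-to-first-event summary. No SAP is shown.

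On follow-up, Section 6.5 plans 10 years. Section 10.6 sizes the Humira arm on 5 years: "Assuming a total of 500 patients with full 5 years of follow up in the Humira arm", then "Allowing for approximately 68% dropout, a total of approximately 1500 patient years exposure in the Humira arm". Under Section 6.1, MTX patients who switch leave the MTX arm and start a new 10-year clock in the Humira arm; no reverse move is described.

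**The concern.** The percent divides patients with an event by all treated patients, however long each was followed. A patient who leaves after one year without an event counts the same as one followed event-free for ten. The result carries no time horizon, and it shrinks as follow-up shortens.

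The primary objective is long-term safety, with MTX as the reference group (Section 5.0). Readers will take the percent of Humira patients with a serious event as the registry's risk and set it beside the MTX percent. The first reading is too low whenever patients leave early. The second can show a difference, or hide one, only because the arms were followed for different lengths of time.

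The rates per 100 patient-years answer a different question. They count events, so several events in one patient and single events in several patients look alike, and they average over time.

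**Working it through.** **1. The plan's own figures.** Section 10.6 takes 500 Humira patients over 5 years (2500 patient-years at most), 68% dropout and about 1500 patient-years. It states that this "will have approximately 97% power", two-sided at 0.05, when the true serious-infection rate is 4.8 per 100 patient-years and the reference, from Study DE038, is 2.8.

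- Expected events in 1500 patient-years: 0.028 × 1500 = 42 and 0.048 × 1500 = 72.
- One-sample Poisson, normal approximation: (72 − 42 − 1.96 × √42) / √72 = 2.04, power 97.9%. The exact test (reject at 56 or more events) gives 97.8%. The stated power is reproduced closely.
- Exposure: a constant leaving rate m with 32% remaining at Year 5 is m = −ln(0.32)/5 = 0.2279 per year. Expected exposure is 500 × 0.68/0.2279 = 1492 patient-years, matching about 1500. Uniform leaving over 5 years gives 2500 × (1 − 0.68/2) = 1650. Simply scaling 2500 by 0.32 gives 800, which does not match. The 68% is therefore best read as the share who have left by Year 5.

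**2. Crude percent against 5-year risk.** Let h be the first-event rate, with leaving independent of events.

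- 5-year risk = 1 − exp(−5h).
- Crude percent, constant leaving = h/(h + m) × [1 − exp(−5(h + m))].
- Crude percent, uniform leaving = 0.32 × risk + 0.68 × [1 − (1 − exp(−5h))/(5h)].

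| h per 100 PY | 5-year risk | Crude, constant leaving | Shortfall | Crude, uniform leaving | Shortfall |
|---|---|---|---|---|---|
| 2.8 | 13.1% | 7.9% | 39.5% | 8.7% | 33% |
| 4.8 | 21.3% | 13.0% | 39.0% | 14.4% | 33% |

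At h = 0.048, constant leaving: 0.048/0.2759 × (1 − exp(−1.379)) = 0.1740 × 0.7483 = 13.0%.

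For rarer events (0.5 to 1 per 100 patient-years) the shortfall is 40% with constant and 34% with uniform leaving. At 30 per 100 it is 32% and 26%.

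**3. Two arms with the same risk.** The documents give no arm-specific dropout, so the leaving rates here are assumed. With h = 4.8 per 100 patient-years in both arms, and 50% against 85% gone by Year 5, the crude percents are 15.6% and 9.9%. The rate stays at 4.8 in both.

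**4. When the rate also moves.** Assume an event rate of 10 per 100 patient-years in year 1 and 2 afterwards, identical in both arms.

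- With 50% gone by Year 5, mean time at risk is 0.934 years in year 1 and 2.673 later: (10 × 0.934 + 2 × 2.673)/3.607 = 4.1.
- With 85% gone, it is 0.832 and 1.408: (10 × 0.832 + 2 × 1.408)/2.240 = 5.0.

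The rate is unaffected by unequal follow-up only if the hazard is constant.

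**The case against.** The strongest reply is that the same sections already plan rates per 100 patient-years with confidence intervals, and that with a constant hazard, as step 2 assumes, these are not biased by dropout. That stands: the plan does adjust for follow-up time. But the rates give neither the proportion of patients affected nor the timing, and step 4 shows that they too can differ between arms with equal hazards.

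A reader might infer that the Section 10.3.1 percent is about 40% too low. The documents do not support that. The 68% is an allowance for Humira exposure over 5 years, whereas Section 10.3.1 continues off drug and through the HCP process for up to 10 years. No rate of loss from observation is given. Even if the same leaving rate ran for 10 years, the crude percent at 2.8 per 100 patient-years would be 10.1%. That is 23% below the 5-year risk of 13.1% and 59% below the 10-year risk of 24.4%.

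A reader might also infer that the arms will differ. One-way switching makes unequal follow-up plausible, but its size is not documented, and the plan specifies no test on these percents. Nor does the plan call the percent a 5-year risk; it attaches no horizon at all.

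The design rates are event rates, used in step 2 as first-event rates. If patients have repeat events, the absolute risks shown are too high; the relative shortfall changes little.

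Finally, time-to-event tables could be placed in the SAP, which is not shown. Their absence from the protocol is therefore weak evidence. The point rests on the measure that Section 10 does specify.

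**Conclusion.** The concern holds as a moderate reporting gap. The crude percent is the only patient-level measure described; it is not a risk at any stated time, and it is not comparable between arms if follow-up differs. As an estimate of a fixed-time risk it is too low whenever some patients leave before that time.

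For the registry treatment-emergent summary (Section 10.3.2) the shortfall against the 5-year risk is about 33–40% at the design rates. This assumes that 68% leave by Year 5, at a constant or uniform rate and independently of events, with a constant first-event hazard. The same reasoning applies to Section 10.3.3, but its clock starts before enrolment, so the figure is less exact there. For Section 10.3.1 the size cannot be derived from the documents. The arm contrasts in steps 3 and 4 are illustrations, not forecasts.

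**What to change.** Keep the counts and the per-patient-year rates. State in the tables that the crude percent is not a risk at a fixed time. Add cumulative incidence of first event by arm, with 95% confidence intervals and numbers at risk:

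- **Method.** Aalen-Johansen with death as the competing event; Kaplan-Meier is enough for death and for any SAE, since a fatal event is itself an SAE.
- **Horizon.** 1, 3, 5 and 10 years for SAE, serious infection, malignancy, CHF and death. The other AESI only to Year 5, because Section 6.0 and Table 1 note f narrow AESI collection after that, except in patients aged 2 to <4 years.
- **Censoring.** Last contact for the observational summary; last dose plus 70 days for the registry treatment-emergent summary, with patients out of the risk set during treatment interruptions.
- **Delayed entry** where time starts before enrolment (Section 10.3.3), since Section 6.1.1 admits patients already up to 24 months, or longer for some rollover patients, into therapy.

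The cost is analysis-plan wording and a few tables, with no new data collection. The limits should be stated with the results:

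- Late estimates rest on few patients.
- HCP onset dates are recorded only where known (Section 7.3).
- HCP follow-up does not collect every SAE (Section 6.0), so a sensitivity analysis censoring at entry to that process is sensible for any SAE and serious infection.
- Censoring at a switch from MTX to Humira may be informative, because switching follows non-response, intolerance or a need for combination therapy. The arm curves are therefore descriptive.
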